7.3 Analysis of Safety

All adverse events collected will be coded using MedDRA, to preferred term and system organ class and summarized for the Safety Analysis Set and de-registered subjects. AEs will be summarized showing the number of events and the number of patients with each event.

A by-patient listing of (serious) adverse events / UADE, including identification of the event by investigator term, date and time started, intensity, relationship to study drug, action taken, and date and time resolved, will be presented in the data listings.

A by-patient listing of deaths will be presented.

Device deficiency is defined as the inadequacy of a medical device with respect to its identity, quality, durability, reliability, safety, or performance. Device deficiencies include malfunctions, use errors, and inadequate labeling.

Device malfunction/deficiencies and any (serious) adverse events associated with device malfunction/deficiencies will be tabulated by treatment arm and overall. All randomized subjects, including de-registered subjects, will be included in the analysis.

7.4 Other subjects related to statistical analysis

1) Handling of Missing Values and Outlier

1. Missing values

Handling of the missing values is indicated in the Statistical Analysis Plan. Final decision will be made at the Case Review Meeting.

2. Outlier

Outlier is not expected in the plan. The effect of the outlier to the analysis will be reviewed when necessary.

2) Change of Data

If bias of data distribution is found, appropriate data will be used instead when necessary.

3) Interim Analysis

No interim analysis will be performed in this trial.

4) Handling of the bail-out lesion

Stents used for bail-out will be included in efficacy and safety analysis.

5) Others

When necessary, additional exploratory analysis will be performed.

7.5 Sample Size Considerations

Power

The Farrington-Manning test, with a TLF_{12} event-rate of 0.058, margin of 0.05, Type I error α of 0.10, and propensity-score matching 1 JNIR to 4 BIONIC patients provides enrollment of 100 subjects will provide 80% power expecting a 5% loss to follow up. We derive the 0.058 event rate from a sample-weighted average of the same 8 related trials used to design BIONICS: SPIRIT (III/IV), PLATINUM, RESOLUT (All Comers / US), TWENTE, and COMPARE (I/II). A margin of 0.05 (5%) , 1.5 times that of BIONICS, leverages a reasonable clinical threshold with safety concerns over sample size. Likewise, propensity-score matching every one JNIR patient to 4 BIONICS patients allows higher power without a higher burden on enrollment.

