6.3.7 Number of Subjects Required to Be Included in the Clinical Investigation

Based on the statistical assumptions described in section 7 enrollment of 100 subjects will provide **80% power** expecting a 5% loss to follow up.

6.4 **Procedures**

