8.5. ACTIVE-CONTROL STUDIES INTENDED TO SHOW NON-INFERIORITY OR EQUIVALENCE

JNIR01 is aimed at assessing TLF at one year with the MedJ-01 stent in a Japanese patient population to show non-inferiority of JNIR01 TLF₁₂ to the BIONICS TLF₁₂.

The non-inferiority margin will be set to 0.05 (5%). This margin, 1.5 times that of BIONICS, leverages a reasonable clinical threshold with safety concerns over sample size.

If the one-sided 90% confidence interval for the upper bound of the difference (JNIR01 TLF₁₂ minus BIONICS TLF₁₂) is less than this pre-specified non-inferiority margin, then the null hypothesis is rejected.

Details of the statistical method used to test non-inferiority are given in Section 15.1.

Document: T:\PROJ\Medinol\CXA27472\06 Biostatistics\Documentation\SAP\Final

1.0_08Aug2018\JNIR01_SAP_Final V1.0_08Aug2018.docx

Author: [name] Version Number: Final V1.0 Version Date: 08Aug2018

Template No: CS TP BS016 Revision 4 Reference: CS WI BS005

Effective Date: 01Apr2016

Copyright © 2009, 2010, 2012, 2016 Quintiles Transnational Corp. All rights reserved.

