15.1.2. PRIMARY ANALYSIS OF PRIMARY EFFICACY VARIABLE

The primary objective of this study is to measure the non-inferiority of JNIR Target Lesion Failure at 12 months (TLF₁₂) to the BIONICS TLF₁₂.

The trial defines the statistical null hypothesis as

 H_{Null} : TLF_{12} (JNIR) > TLF_{12} (BIONICS) + δ

 $H_{Alternative}$: TLF_{12} (JNIR) $\leq TLF_{12}$ (BIONICS) + δ

or in terms of absolute event-rate difference

 H_{Null} : TLF_{12} (JNIR) - TLF_{12} (BIONICS) > δ

H_{Alternative}: TLF₁₂ (JNIR) - TLF₁₂ (BIONICS) $\leq \delta$

where δ =0.05 is the margin of non-inferiority (refer to Section 8.5).

The primary efficacy analysis will be performed for the FAS. Only patients with appropriate follow up (>=335 days post procedure) or who experienced the primary endpoint by the end of the 365 day visit window (day 379) will be included.

A comparison of the proportion of patients with TLF at 12 months will be performed using the Farrington-Manning test of non-inferiority for two binomial proportions with a non-inferiority margin of δ =0.05 at the 0.1 level of significance (one-sided) [3].

The Farrington-Manning test statistic will be calculated as follows:

$$\tau = \frac{\text{TLF}_{12} \text{ (JNIR)} - \text{TLF}_{12} \text{ (BIONICS)} - \delta}{\sqrt{\frac{\text{TLF}_{12} \text{ (JNIR)}[1 - \text{TLF}_{12} \text{ (JNIR)}]}{N(\text{JNIR})} + \frac{\text{TLF}_{12} \text{ (BIONICS)}[1 - \text{TLF}_{12} \text{ (BIONICS)}]}{N(\text{BIONICS})}}$$

where N(JNIR) and N(BIONICS) are the number of patients from the JNIR trial and BIONICS trial, respectively.

Propensity score matching will identify a covariate-unbiased population of patients between the JNIR and BIONICS patient population. To maximize power and take advantage of the large BIONICS study, 4:1 matching will be done. This covariate-unbiased population will be used to calculate TLF_{12} (BIONICS) and N(BIONICS) in the Farrington-Manning test statistic.

The probability a patient (x) belongs to JNIR versus BIONICS, conditional on a set of potential confounding covariates (C), defines the propensity score $\rho(x \mid C)$. Logistic regression will model this probability as

$$\rho(\mathbf{x} \mid \mathbf{C}) = \mathrm{logit}^{-1} \left(\sum_{c \in C} c \right)$$

where $logit^{-1}(x) = \frac{1}{1 + e^{-x}}$.

Matching of patients from JNIR to patients from BIONICS will be done using the following covariates which

Document: T:\PROJ\Medinol\CXA27472\06 Biostatistics\Documentation\SAP\Final

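### The stated 80% power does not follow from the plan's own inputs: they give about 61–64% with the Farrington-Manning test and 70–72% with the printed formula

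*Protocol*

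**What the plan says.** Protocol section 7.5 gives every input to the calculation: "The Farrington-Manning test, with a TLF_{12} event-rate of 0.058, margin of 0.05, Type I error α of 0.10", matching of one JNIR patient to four BIONICS patients, and the conclusion that "enrollment of 100 subjects will provide 80% power expecting a 5% loss to follow up". Section 6.3.7 relies on the same calculation: "Based on the statistical assumptions described in section 7 enrollment of 100 subjects will provide" 80% power, again with 5% loss.

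The SAP does not restate the power, but it settles what section 7.5 leaves open. Section 15.1.2 specifies the "Farrington-Manning test of non-inferiority for two binomial proportions with a non-inferiority margin of δ =0.05 at the 0.1 level of significance (one-sided"). Section 8.5 confirms the margin and bases the decision on the upper bound of a one-sided 90% confidence interval. Section 15.1.2 also keeps in the primary analysis only patients with at least 335 days of follow-up or a primary endpoint event by day 379, and matches four BIONICS patients to each JNIR patient.

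**The concern.** All the inputs are stated, so the 80% can be checked directly, and it looks too high for 95 evaluable patients at this event rate and margin.

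The comparison of TLF at 12 months is the only formal test in the trial (SAP sections 7.5 and 8.4). The protocol's revision summary records that the sample size went from 86 to 100, and that section 7 was revised, at the regulator's request. The power statement is therefore part of the design justification that a regulator or review board would read. If it is wrong, anyone interpreting a failed or borderline result will misjudge how likely failure was with a stent performing as well as in BIONICS. Low power does not itself raise the risk of a false non-inferiority claim. What is at stake is the risk of missing a true one.

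**Working it through.** **Inputs**

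- TLF rate 0.058 (Protocol 7.5). Only one rate is given, so it is taken as the true rate in both groups.
- Margin 0.05 (Protocol 7.5; SAP 8.5 and 15.1.2).
- Alpha 0.10, one-sided (SAP 15.1.2), so z = 1.2816.
- 100 enrolled with 5% loss gives 95 evaluable JNIR patients. At 1:4 that is 380 BIONICS patients.

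Both documents name the Farrington-Manning test, whose variance is estimated under the null restriction. The statistic they print uses the unrestricted variance of the observed rates. Both versions were checked.

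**Printed formula (unrestricted variance)**

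SE = √[0.058 × 0.942 × (1/95 + 1/380)] = 0.02681

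Power = Φ(0.05/0.02681 − 1.2816) = Φ(0.583) = **72.0%**

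Exact binomial enumeration of the same statistic gives **70.0%**.

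**Farrington-Manning (restricted variance)**

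With the difference fixed at 0.05, the restricted rates are 0.1021 (JNIR) and 0.0521 (BIONICS).

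SE under the null = √[0.1021 × 0.8979/95 + 0.0521 × 0.9479/380] = 0.03308

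Power = Φ[(0.05 − 1.2816 × 0.03308)/0.02681] = Φ(0.283) = **61.2%**

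Exact enumeration gives **64.4%**.

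**Attempts to recover 80%**

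| Reading | Farrington-Manning, approx. / exact | Printed formula, approx. / exact |
|---|---|---|
| As planned, 95:380 | 61.2% / 64.4% | 72.0% / 70.0% |
| No loss, 100:400 | 63.0% / 66.1% | 73.6% / 71.5% |
| Alpha 0.10 read as two-sided, 95:380 | 43.5% / – | 58.7% / – |
| 95 JNIR against an unlimited BIONICS group | – | 78.9% / – |
| 100 JNIR against 1919 BIONICS patients (all enrolled, both arms) | 66.0% / 67.5% | 78.9% / 75.7% |

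**Evaluable patients needed for 80% at the stated inputs**

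- Unrestricted formula: (1.2816 + 0.8416)² × 0.058 × 0.942 × 1.25/0.05² = 123.1, so 124 evaluable and 131 enrolled (124/0.95). This is an approximation; exact power of the printed statistic at 124:496 is 77.5%.
- Farrington-Manning: about 161 evaluable, so 170 enrolled (161/0.95). Exact power at 161:644 is 80.8%.

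**TLF rate at which 95:380 would reach 80%**

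About 4.4% (unrestricted approximation), 3.7% (printed statistic, exact) or 2.6% (Farrington-Manning, exact). The plan assumes 5.8%.

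**The case against.** The case for leniency has four parts.

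- **Some calculations do land near 80%.** Reversing the allocation to 380 JNIR and 95 BIONICS patients gives 79.5% (exact 80.2%) for Farrington-Manning. One-sided alpha 0.20 gives 79.6%. An unrestricted comparison of 100 JNIR patients with a fixed 5.8% gives 80.4%. Each contradicts the plan's ratio, alpha, or two-sample comparison and loss allowance. The reversed ratio is a plausible source of the error, but the documents do not show the calculation.
- **Equal true rates are an assumption.** With BIONICS at 5.8% and JNIR truly at 4.5%, Farrington-Manning power would be about 80% (exact 82%). The plan claims no such advantage, and a single stated rate is naturally read as common to both groups.
- **The replacement figure depends on the statistic.** This stands. A program written from the printed formula has 70% power, not 64%. Part of that higher figure comes from a looser test: at true rates of 10.8% and 5.8% with 95:380, its exact type I error is 12.8%, against 10.1% for Farrington-Manning.
- **The sample size may not have rested on this sentence.** The change to 100 was made at the regulator's request. That bears on how 100 was chosen, not on whether the 80% is correct.

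**Conclusion.** The power statement is wrong as written. At the plan's inputs the design has 61–64% power with the test it names and 70–72% with the formula it prints, a shortfall of 8 to 19 percentage points. The type II error is about 36–39% or 28–30% respectively, against the stated 20%. No reading that keeps the stated inputs reaches 80%.

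This rests on equal true TLF rates of 5.8%, one-sided alpha of 0.10, and 95 evaluable JNIR patients with 380 matches. Any effect of quintile matching on the variance is ignored, and the plan's power statement does not mention one.

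**What to change.** Keep 100 patients, the margin and alpha. In Protocol sections 6.3.7 and 7.5, replace the 80% with the power of the named test: about 64% (exact Farrington-Manning; 61% by normal approximation) for 95 JNIR and 380 BIONICS patients at a TLF rate of 5.8% in both groups. State the equal-rates assumption and add a short table labelled with the test it describes:

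| TLF rate, both groups | Exact Farrington-Manning power, 95:380 |
|---|---|
| 2.6% | 81% |
| 4.0% | 72% |
| 5.8% | 64% |

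The figures must match the statistic that will be programmed. If the sponsor decides that the printed unrestricted statistic is the one to be used, the corresponding exact values are 88%, 78% and 70%, and the text should then not call it Farrington-Manning.

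The cost is one sentence in each of two sections and a three-row table. The stated power becomes less favourable. No patients are added.

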8 DATA MANAGEMENT

8.1 Procedures Used for Data Review, Database Cleaning, and Issuing and Resolving Data Queries

Medidata will provide Rave electronic data capture (EDC) system for the trial. The sites are responsible for completing the clinical electronic CRF (eCRF) from Rave. The data cleaning routines are performed during data entry through automatic edit checks that occur during data entry by the sites into Rave. The auto-queries are generated by Rave and are resolved by the site. Those auto-queries will be cleared when the revised data entry meets the edit check criteria or the monitor accepts the revised entry. The manual queries are created by the site monitors. The Data Manager can create manual queries on data as well for the sites to review. Rave system flags the records with data queries which are resolved by the site, and the manual queries are cleared by the originating personnel. Tracking of data cleaning query status is facilitated by standard reports from Rave. Data listings needed for data review are created outside of Rave. Please see the separate Data Management Plan for specific details.

8.2 Procedures for Verification, Validation, and Securing of Electronic Clinical Data Systems

Rave EDC system hosted by Medidata will be programmed and maintained by Quintiles DM. Rave EDC system will enforce restricted access control mechanisms under the management of Quintiles CPM. And will incorporate encrypted point-to-point data transfer via secure HTTP protocols. Trial Investigators/sites will enter data online; data will be stored at a secure and confidential location, and will be downloaded via SAS on Demand function in Rave for review and analyses on a regular basis. Further details of verification, validation, and securing of electronic clinical data systems can be found in the trial specific Data Management Plan.

8.3 **Procedures for Data Retention and Specified Retention Period**

All core laboratories and clinical sites will maintain study records pertaining to this trial for 15 years following trial completion, or as otherwise instructed by the Sponsor, or per local requirements whichever is longer.

ICH guidelines require that essential documents be retained until at least 2 years after the last approval of a marketing application in an ICH region and until there are no pending or contemplated marketing applications in an ICH region or at least 2 years have elapsed since the formal discontinuation of clinical development of the investigational product.

To comply with these requirements, the investigator will not dispose of any records relevant to this trial without either (1) written permission from the Sponsor, or (2) providing an opportunity for the Sponsor to archive the records. The investigator shall take responsibility for maintaining adequate and accurate source documents of all observations and data generated as required during this trial, including any data clarification forms received from the Sponsor or its designees. Such documentation is subject to inspection by the Sponsor or its agents, the IRB, or other regulatory agencies.

The Investigator will be notified by the Sponsor of the date of marketing approval or discontinuation of the trial. The Investigator will obtain permission from the Sponsor in writing before destroying or transferring control of any trial records.

8.4 Other Aspects of Clinical Quality Assurance

8.4.1 Clinical Events Committee

The Clinical Events Committee (CEC) will be comprised of cardiologists who are not participants in the trial and who have no conflict of interest with the trial or the trial sponsor. All members of the CEC will be blinded to the primary results of the trial.

The CEC will be responsible for the adjudication of the clinical trial endpoint events. At the onset of the trial, the CEC will establish explicit rules outlining the process for adjudication and the algorithms followed in order to classify a clinical endpoint event. The CEC will also review and rule on all deaths that occur throughout the trial. In addition, the CEC will review and adjudicate device non-success. Definitions are provided in Section 21.1.

Once the specific criteria for clinical endpoints are established by the CEC, Cardiovascular Research Foundation will be responsible for preparing all clinical endpoint event dossiers and for the conduct of the CEC meetings.

8.4.2 Selection of Clinical Sites and Investigators

The sponsor will select Investigators who are qualified by training and experience, and are legally entitled to perform clinical research and to participate in the investigation of the study device. Sites will be selected based upon review of a recent site assessment and the qualifications of the Primary Investigator at the site.

8.4.3 Clinical Investigational Plan and Informed Consent Approval at Investigative Sites

Institutional Review Board (IRB) approval for the clinical investigation plan, informed consent form and other trial related documents will be obtained by the head of medical institution at each investigational site prior to participation in this trial. The approval letter must be signed by the IRB chairperson or authorized representative prior to the start of this trial and a copy must be provided to the Sponsor. In addition, the Investigator or designee will provide the Sponsor with all required documentation necessary for initial and ongoing trial approval at their site.

In accordance with the investigational site IRB requirements, the Investigator will (a) advise the IRB of the progress of this trial on a regular basis until trial completion. The head of medical institution will (b) obtain written IRB approval at predetermined time points to continue the trial; and (c) submit any amendments to the clinical investigation plan as well as associated informed consent form changes and obtain written IRB approval obtained prior to implementation.

8.4.4 Source Documents

For the duration of the trial, the Investigator will maintain complete and accurate documentation including but not limited to medical records, trial progress records, laboratory reports, case report forms, signed informed consent forms, device accountability records, and correspondence with the IRB and Sponsor, adverse event reports, and information regarding subject discontinuation or completion of the trial.

Source documents are defined as original documents, data, and records. Regulations require that the Investigator maintain source documents in the subject's medical records, which confirm the data entered on the case report forms. All data provided to the Sponsor on the CRFs must be also part of the subject's medical record as noted in Section 6.5.2.

8.4.5 Case Report Form (CRF) Completion

Primary data collection based on source-documented hospital and/or clinic chart reviews will be performed clearly and accurately by site personnel trained on the clinical investigation plan and CRF completion. The Sponsor or designee will provide clinical monitoring as specified in Section 6.5.1.

9 AMENDMENTS TO CIP

If the clinical investigational plan needs an amendment, the Sponsor is required to submit such amendment to the Regulatory Agencies and/or other regulating body in each participating country for approval. Approved clinical investigational plan amendments will be provided to the Investigators by the Sponsor prior to implementing the amendment. For administrative changes the Primary Investigator is responsible for notifying the IRB of the clinical investigational plan amendment. For changes involving subject care or safety the Primary Investigator is responsible for obtaining IRB approval of the clinical investigational plan amendment according to the instructions provided by the Sponsor with the clinical investigational plan amendment.

Acknowledgement/approval by the IRB of the clinical investigational plan amendment must be documented in writing prior to implementation of the clinical investigation plan amendment. Copies of this documentation must also be provided to the Sponsor.

10 DEVIATIONS FROM CLINICAL INVESTIGATION PLAN

10.1 Statement Specifying That the Investigator Is Not Allowed to Deviate from the CIP

No investigative procedures other than those defined in this clinical investigational plan will be undertaken on the enrolled subjects without the written agreement of the IRB and Sponsor.

It is the Investigator's responsibility to ensure that there are no deviations from the clinical investigational plan and full compliance with all established procedures of the IRB is maintained. The Investigator will not deviate from the clinical investigational plan for any reason except in cases of medical emergencies, when the deviation is necessary to protect the life or physical well-being of the subject.

10.2 Procedures for Recording, Reporting, and Analyzing CIP Deviations

A deviation is an instance(s) of failure to follow, intentionally or unintentionally, the requirements of the Clinical Investigation Plan. All deviations must be reported to the Sponsor. The occurrence of clinical investigational plan deviations will be monitored by the Sponsor or designee. It is the Investigator's responsibility to inform their IRB of clinical investigational plan deviations in accordance with their specific IRB reporting policies and procedures.

In the event that an investigative site does not comply with the Investigator Agreement or clinical investigational plan, the Sponsor will notify the Investigator of the site's non-compliance. Continued non-compliance may result in further escalation in accordance with the Sponsor's standard procedures.

10.3 Notification Requirements and Time Frames

Major protocol deviations shall be notified to the trial Sponsor and Ethics Committee. Sponsor nominated personnel will also observe and record any protocol deviations during routine monitoring visits and follow up accordingly.

10.4 Corrective and Preventative Actions and Principal Investigator Disqualification Criteria

Protocol deviations and site/PI non-compliance will be closely monitored by the Sponsor and appointed study personnel. Identifying deviations and taking corrective actions at the earliest possible stage increases the potential for clinical trial success and reduces patient risk. The initiation of a corrective and preventative action (CAPA) to investigate and establish corrective actions may be required in some cases. The Sponsor reserves the right to close a clinical study site or replace a PI if non-compliance is observed

